3.3. Sample Size Considerations

3.3.1. Sample Size Justifications

Assuming a difference in change from baseline in pVO₂ of 1.5 mL/kg/min for CK-3773274 compared to placebo, a standard deviation (SD) of 3.5 mL/kg/min, accounting for limiting beta-blocker use (less than ~70%), limiting exercise modality of bicycle (less than ~50%) and 10% of patients missing change from baseline data of the primary endpoint, a sample size of 270 patients at randomization ratio of 1:1 (approximately 135 randomized to CK-3773274 and 135 randomized to placebo) provides more than 90% power to detect the difference in pVO₂ change from baseline to Week 24 with a 2-sided type I error of 0.05.

During the study, Cytokinetics will periodically assess in a blinded fashion the aggregate pooled missing data rate and overall pooled SD for the change from baseline in pVO₂ at Week 24. If the pooled SD is larger than expected, Cytokinetics may consider increasing the sample size once in order to maintain the intended power.

3.4. Randomization

All eligible patients will be centrally assigned to randomized IP using the IWRS. Randomization will be stratified by use of beta-blockers (yes or no) and CPET exercise modality (treadmill or bicycle) and implemented in the IWRS.

3.5. Clinical Assessments

3.5.1. Efficacy Assessments

Efficacy assessments include CPET, echocardiography, NYHA classification, patient-reported outcomes (KCCQ, EQ-5D-5L), Patient Global Impression of Change scale (PGI-C) and SAQ-7, and clinical global impression scale (CGI). CMR measurements will be assessed in patients included in CMR sub-study.

3.5.1.1. Echocardiography

Echocardiography will be done during screening, prior to dosing on Day 1, and 2 hours after dosing in the clinic on Weeks 2, 4, 6, 8, 12, 16, 20, 24, and 28.

Site read echocardiographic assessments include LVEF, resting and Valsalva LVOT at each visit. Unless otherwise specified, echocardiographic variables will be based on the core echocardiography laboratory assessments. [Table 2](#) below lists the echocardiography parameters from core lab. A full list of echocardiography parameters is specified in the data transfer agreement from core lab.

Table 2: Echocardiographic Variables and Names

Endpoint Names
Variables Describing LV Structure
Left ventricular end diastolic diameter
Left ventricular end diastolic volume Index

Table 2: Echocardiographic Variables and Names (Continued)

Endpoint Names
Left Ventricular End Systolic Volume Index
Left ventricular end systolic diameter
Left Ventricular Posterior Wall Thickness, End-diastole
LV Mass indexed
Interventricular Septum Thickness, End-Diastole
Left ventricular Maximal wall thickness
Left ventricular relative wall thickness
Variable Describing LV Systolic Function
Left ventricular ejection fraction
Left ventricular fractional shortening
Left ventricular stroke volume Index
Left ventricular cardiac output Index
Left Ventricular Isovolumetric Contraction Time
Left Ventricular Isovolumetric Relaxation Time
Left Ventricular Ejection Time
Left Ventricular Myocardial Performance Index
Left Ventricular Outflow Tract Velocity Time Integral
Left Ventricular Global Longitudinal Strain
Left Ventricular Global Circumferential Strain
Variables Describing LV Diastolic Function
Peak E Wave Velocity
Peak A Wave Velocity
Mitral Lateral Annular Early Diastolic Velocity
Mitral Septal Annular Early Diastolic Velocity
Mitral E/A Wave Velocity Ratio
Mitral E Wave to Lateral Annular Early Diastolic Velocity Ratio
Mitral E Wave to Septal Annular Early Diastolic Velocity Ratio
LVOT Dynamic Gradient Assessment Variables
Peak Left Ventricular Outflow Tract Pressure Gradient at Rest
Peak Left Ventricular Outflow Tract Pressure Gradient during Valsalva Maneuver

Table 2: Echocardiographic Variables and Names (Continued)

Endpoint Names
Variables Describing LA Size and Function
Left Atrial Width
Left Atrial Volume Index
Variables Describing RV Size and Function
Right Ventricular Outflow Tract Velocity Time Integral
Right Ventricular Myocardial Performance Index
Tricuspid annular plane systolic excursion
Valvular Assessment Variables
Presence of Mitral Regurgitation
Mitral Regurgitation Jet Area to Left Atrial Area Ratio
Presence of Mitral Systolic Anterior Motion

3.5.1.2. Patient-Reported Outcomes

KCCQ and EQ-5D-5L will be assessed at Day 1, Weeks 2, 4, 6, 8, 12, 16, 20, 24 and 28 (4 weeks after last dose at end of the study). SAQ-7 will be assessed at Day 1, Weeks 4, 8, 12, 16, 20, 24 and 28. PGI-C will be assessed at the Week 24. Algorithms to derive the scores KCCQ, EQ-5D-5L and SAQ-7 are in [Section 11.1](#).

EQ-5D-5L and EQ-VAS

The instrument EQ-5D is a standardized measure of health status for clinical and economic appraisal ([EuroQol Group 1990](#)), which consists of two parts: a short descriptive system questionnaire (EQ-5D-3L) and a visual analogue scale (EQ-VAS).

EQ-5D-5L is the 5-level version of EQ-5D introduced to improve the instrument's sensitivity and to reduce ceiling effects ([EuroQol Group 2009](#)). The descriptive system comprises 5 dimensions: mobility, self-care, usual activities, pain/discomfort and anxiety/depression. Each dimension has 5 levels indicating no problems, slight problems, moderate problems, severe problems or extreme problems. Five responses with a response from each of the 5 dimensions form a 5-digit number that defines a patient's health state profile. A health state can potentially be assigned a summary index score based on societal preference weights (societal perspective) for the health state. The health state preferences often represent national or regional values and can therefore differ between countries/regions. The health state index scores will be calculated using the composite time trade-off (cTTO) method based on the United States valuation of EQ-5D-5L ([Pickard 2019](#)) for patients from the United States and for the FAS. The health state index score ranges from less than 0 to 1 with higher scores indicating higher health utility; a score 0 represents death, negative values represent worse than death, and 1 represents full health.

EQ-VAS rates a patient's perceived health on a vertical visual analogue scale from 0 to 100, where 0 represents the worst imaginable health and 100 represents the best imaginable health.

The VAS can be used as a quantitative measure of health outcome that reflects the patient’s own judgement.

3.5.1.3. CMR Assessments

A CMR imaging sub-study will assess the effects of administration of CK-3773274 dosing on cardiac morphology, function, and fibrosis in approximately 100 oHCM patients who are eligible and consent to participate. CMR will be performed during screening period and Week 24. CMR parameters are listed below in [Table 3](#) and a final list of CMR parameters is specified in the data transfer agreement from core lab.

Table 3: CMR Parameters

LV Parameters
LVM - Left Ventricular Mass
LVMI Left Ventricular Mass Index
LVEDV - Left Ventricular End Diastolic Volume
LVEDVI - Left Ventricular End Diastolic Volume Index
LVESV - Left Ventricular End Systolic Volume
LVESVI - Left Ventricular End Systolic Volume Index
LVSV– Left Ventricular Stroke Volume=LVEDV-LVESV
LVSVI = Left Ventricular Stroke Volume Index=LVSV/Body Surface Area (mm2)
LVEF - Left ventricular Ejection Fraction
CO - Cardiac Output = Heart Rate x Stroke Volume
CI - Cardiac Index = Heart Rate x Stroke volume/Body Surface Area (m2)
LV maximal septal wall thickness
LV maximal lateral wall thickness
LV maximal wall thickness (each of 16 segments)
Overall LV maximal wall thickness (highest across all 16 segments)
LGE mass (g) (Global mass of LGE 6SD)
LGE mass % (as % of LV mass) (Global percent of LGE 6SD)
Global average ECVF

Table 3: CMR Parameters (Continued)

LV Parameters
LV Segmental assessment of ECVF
Global Native T1
Extracellular volume (ECV)
Global ECV mass
Global ECV mass index
ECVF normalized for height
HCM morphology (isolated basal septal hypertrophy, reverse septal curvature, apical, midcavity obstruction without apical aneurysm, midcavity obstruction with apical aneurysm, concentric, other
RV Parameters
RV end-diastolic volume (RVEDV)
RV end-diastolic volume index (RVEDVI)
RV end-systolic volume (RVESV)
RV end-systolic volume index (RVESVI)
RV stroke volume (RVSV)
RV stroke volume index (RVSVI)
RV ejection fraction (RVEF)
LA parameters
LA volume maximum
LA volume maximum index
LA reservoir amount
LA reservoir percent
LA contractile amount
LA contractile percent
LA total amount
LA total percent
LA global longitudinal strain
Mitral Valve Parameters
Exploratory Mitral Valve Regurgitation Measurements
Mitral regurgitation volume
Mitral regurgitation, regurgitation fraction

3.5.1.4. CPET Assessments

All patients will undergo CPET with gas-exchange analysis and the methodology will be standardized across all sites as specified in the CPET manual. Patients must use the same testing modality for all exercise tests during the trial. CPET are done at baseline and Week 24 post randomization. CPET parameters are listed below. A full list of CPET parameters is specified in the data transfer agreement from core lab.

- Workload
- Exercise Duration
- % of Predicted Oxygen Uptake
- Circulatory Power
- Predicted Oxygen Uptake
- Peak Oxygen Uptake per Kilogram
- Peak RER
- Oxygen Uptake Efficiency Slope
- Ventilatory Efficiency
- Anaerobic Threshold
- Aerobic Efficiency

3.5.2. Safety Assessments

Safety assessments include adverse events and serious adverse events (SAEs), ICD discharge, LVEF < 50% and <40%, electrocardiograms, laboratory assessments, physical examinations, and vital signs.

3.5.3. Pharmacokinetics Assessments

Blood samples will be collected to evaluate plasma concentrations of CK-3773274 at pre-dose and 2 hours post-dose at Day 1, Weeks 2, 4, 6, 8, 12, 16, 20 and 24.

4. PLANNED ANALYSES

4.1. Interim Analyses

No interim analysis is planned for this study.

4.2. Final Analyses

The final analysis will occur after all patients randomized in the study have completed the study including the 4-week safety follow up, all data has been entered into the clinical database, verified, and locked. Unblinding for the final analysis will occur after the database lock.

5. GENERAL CONSIDERATIONS FOR DATA ANALYSES AND HANDLING

5.1. General Summary Table and Individual Subject Data Listing Considerations

Descriptive statistics to be presented in a table include number of observations, mean, median, standard deviation, 1st and 3rd quartiles, minimum and maximum for continuous variables, and count of patients and the percentage for categorical variables. For variables that lognormal distribution assumptions may be appropriate geometric mean, and geometric coefficient of variation (CV%) will also be displayed. Geometric CV (%) will be derived as $100\% \times \sqrt{\exp(s^2) - 1}$, where s is the standard deviation of the natural logarithm (ln) transformed data.

For model-based analysis, least squares means (LSM), difference of least squares means between treatments, their standard errors and 95% confidence intervals (CI), and two-sided p-values for the statistical inferences will be presented.

Selected listings may be generated to include patient identifier (ID), demographics, randomized treatment group and other relevant items, and sorted by randomized treatment group, patient ID and date of assessment.

5.2. General Post Text Summary Table and Individual Subject Data Listing Format Considerations

Post text tables and individual subject data listings are prepared according to ICH Guideline E3. In general, summary and analysis tables will be presented by treatment groups and highest dose level administered.

5.3. Data Management

Data will be entered into the clinical database with programmed edit checks and manual data review to ensure integrity. The data will be reviewed and cleaned according to a data management plan. Clinical safety laboratory, ECG, Pharmacokinetics (PK) data, CMR, CPET and echocardiography will be provided per the pre-specified data transfer agreement from external laboratories.

5.4. Data Presentation Conventions

The following conventions will be applied to data presentations:

- For continuous variables, mean and median values are formatted to one more decimal place than the measured value. Standard deviation values are formatted to two more decimal places than the measured value. Minimum and maximum values are presented with the same number of decimal places as the measured value. For the statistical analyses results that are on the same scale as a measured value (e.g., change from baseline or treatment difference estimates), the LSM estimates and LSM estimate 95% CI boundary values will be formatted to one more decimal place than the measured value; Standard error of the mean (SEM) estimates will be formatted to two more decimal

places than the measured values. GLSM estimates for the proportional change from baseline, proportional change treatment ratios, odds ratios, and the corresponding 95% CIs will be presented with two decimal places.

- For categorical variables, the count and percentage of responses are presented in the form XX (XX.X%) where the percentage is in the parentheses.
- Date variables are formatted as YYYY-MM-DD for presentation. Time is formatted in military time as HH:MM for presentation.
- P-values, if applicable, will be presented to 3 decimal places. If the p-value is less than 0.0001 then it will be presented as <0.0001. If the rounded result is a value of 1.000, it will be displayed as >0.999.
- Unless otherwise stated, any statistical tests performed will use 2-sided tests at the 0.05 significance level.

The table and listing shells and table of contents provide the expected layout and titles of the tables, listings and figures. Any changes to format, layout, titles, numbering, or any other minor deviation will not necessitate a revision to the SAP, nor will it be considered a deviation from planned analyses. Only substantial deviation in the analysis methods will require an SAP revision or a change to planned analysis documented in the CSR.

5.5. Analysis Populations

5.5.1. All Screened Patients

All patients who signed the informed consent form (ICF) are included in the All Screened Patients Set. Patients who gave informed consent but are not randomized are considered screen failures. The following reasons for screen failures are collected: inclusion/exclusion criteria (including specific criteria not met), principal investigator decision, subject decision, lost to follow up, and other. For patients who are screen failures, the reasons for failing will be summarized.

5.5.2. All Randomized Set

All Randomized Set includes patients who are randomized to receive CK-3773274 or placebo.

5.5.3. Safety Analysis Set

Safety analyses will be performed on the safety analysis set (SAF), which includes all randomized patients who receive at least one dose of IP, CK-3773274 or placebo. Unless otherwise specified, for safety analyses, subjects will be grouped according to their randomized treatment group assignment with the following exception: if a subject receives treatment throughout the study that is different than the randomized treatment group assignment, then the subject will be grouped by the actual treatment group.

5.5.4. Full Analysis Set

Efficacy analyses will be performed on the full analysis set (FAS), which includes all randomized patients. Patients will be analyzed according to their randomized treatment group assignments.

5.5.5. Pharmacokinetics Analysis Set

All randomized patients who have at least one evaluable plasma concentration of CK-3773274, provided they have no major protocol deviations that could affect the PK of CK-3773274.

5.6. Baseline Definition

Unless otherwise specified, baseline is defined as the last available measurement taken prior to administration of the first dose of study drug. Baseline for KCCQ, EQ-5D-5L and SAQ-7 are assessments performed on Day 1. The assessments collected on the same date as the first dose of the IP that do not have assessment time are considered to have occurred prior to the first dose.

5.7. Derived and Transformed Data

5.7.1. Baseline Age

Age will be calculated as follows:

Age (years) = year of screening date – year of birth,

Patient age will be categorized as < 65 years or ≥ 65 years.

5.7.2. Body Measurements Variable Derivation

Baseline body surface area (BSA) will be calculated using the weight and height at screening using the DuBois and DuBois formula and rounded to two decimal points for the presentation of results:

$$\text{BSA (m}^2\text{)} = 0.007184 * (\text{weight (kg)}^{0.425} * \text{height (cm)}^{0.725}).$$

5.7.3. Study Day

If the date of interest occurs on or after the first dose date, then study day will be calculated as (date of interest – date of first dose) + 1. If the date of interest occurs prior to the first dose date, then study day will be calculated as (date of interest – date of first dose). There is no study day 0.

5.7.4. Change from Baseline

Change from baseline is calculated as (post baseline value – baseline value).

Percent change from baseline is calculated as (change from baseline / baseline value) x 100%.

Proportional change from baseline is calculated as (post-baseline result/baseline value).

If either the baseline or the post-baseline value is missing, the change from baseline and percentage change from baseline will be set to missing.

5.7.5. Summary Scores for Patient Reported Outcomes (PRO)

Calculations of summary scores for KCCQ, SAQ-7 and EQ-5D-5L are specified in [Section 11.1](#).

5.7.6. Analysis Windows

Since study visits do not always take place exactly as scheduled per protocol, it is necessary to assign the actual observation dates to analysis windows for analysis purposes.

For data collected at a scheduled post baseline visit, the analysis visit will be assigned based on the scheduled nominal visit as collected on the eCRF.

For unscheduled or early discontinuation post baseline visits, measurements taken on or after the first dose of study drug will be assigned to an analysis window using defined lower and upper bounds for each analysis window. Measurements assigned in an analysis window will have study day greater than or equal to the lower bound but no greater than the upper bound of the analysis window. The lower bound and the upper bound for the analysis windows are defined as the midpoints between the scheduled visits for all assessments (see [Section 11.4](#)).

Visits are identified as the nominal visits according to the eCRFs. Each visit will be identified with the visit descriptor (eg, “Week 24”).

5.7.7. Multiple Assessments

Once analysis windows are assigned, a patient’s individual analysis window could potentially contain more than one visit. Records from all visits, including scheduled, unscheduled and early discontinuation visits could be flagged as the “analyzed record” within the analysis window, although the records from scheduled visit will take priority.

In the event of multiple visits falling within an analysis window, the following rules will be used in sequence to determine the “analyzed record” for the analysis window:

- If a scheduled visit occurred during the analysis window, then the measurement taken from the scheduled visit will be used.
- If no scheduled visit occurred during the analysis window, the measurement taken closest to the scheduled day will be used as the “analyzed record.”
- If no scheduled visit occurred during the analysis window and there is a tie between unscheduled visits in the number of days before and after the scheduled day, measurements from the later visit will be used as the “analyzed record.”

For analyses by visit, only the “analyzed record” within each analysis window and the visit will be summarized in a table. Only protocol specified visits will be presented in the summary table. If there are other visit records within the analysis window, they will only be included in data listings.

5.7.8. Other Study Related Definitions

Actual Dose Group

Patients in the aficamten actual treatment group will be identified as 5 mg, 10 mg, 15 mg, 20mg or discontinuing IP prior to dose adjustment based on the dose assigned at Week 8. If a patient discontinues IP prior to the start of Week 8 (IWRS Week 8 dispensation), then the subject will be

identified as discontinued IP prior to achieve stable dose. The actual dose group may be used in selected displays.

Investigational Product Exposure Period

For subjects dosed with IP:

$[(\text{Last IP administration date} - \text{date of Study Day 1}) + 1]/7$ (in weeks)

Interruptions recorded in the eCRF page will be excluded from the expected dose calculation.

Treatment-emergent Adverse Event

For the purpose of reporting, an investigator-reported event starting on or after first dose of IP and up to and including 28 days after the last dose date of IP will be labeled as a treatment-emergent AE.

Last Titrated Dose

Last titrated dose is defined as the last titrated dose assigned to the patient during the 24 Week treatment period.

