6.6.1.1. Week 2 Visit

After randomization each patient will receive Dose 1 once daily for two weeks. At the Week 2 visit, the patient will have an echocardiogram 2 hours following administration of their dose of IP. Patients will up-titrate to Dose 2 if the following conditions are met on echocardiography:

- Post-Valsalva LVOT-G ≥ 30 mmHg, and the biplane LVEF $\geq 55\%$

Otherwise, the patient will remain on Dose 1.

If LVEF is $< 50\%$ at Week 2, the IWRS will assign the patient to placebo.

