6.6.1.3. Week 6 Visit

After 2 more weeks on the assigned dose, at the Week 6 visit each patient will have an echocardiogram 2 hours following administration of their dose of IP. Patients will up-titrate to the next higher dose if the following conditions are met on echocardiography:

- Post-Valsalva LVOT-G ≥ 30 mmHg, and the biplane LVEF $\geq 55\%$

Otherwise, the patient will remain on the same dose.

If LVEF is $< 50\%$ at Week 6, the IWRS will assign the patient to the prior dose level or to placebo if the patient was on Dose 1.

Table 4: Echocardiogram Criteria for Scheduled Dose Titrations

Echocardiogram Criteria for Scheduled Dose Titrations in Weeks 2, 4, and 6

Biplane LVEF		Post-Valsalva LVOT-G	Action
$< 50\%$			Reduce Dose ^a
$\geq 50\% - 55\%$			No Dose Change
$\geq 55\%$	and	< 30 mmHg	No Dose Change
$\geq 55\%$	and	≥ 30 mmHg	Increase Dose

^a Once a patient's IP dose is down titrated, no further escalation is permitted. If LVEF $< 50\%$ on 5 mg, the patient will receive placebo.

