7.1. Temporary IP Interruption

Initially, any IP interruption should be considered temporary unless permanent IP discontinuation is mandated by the protocol.

A temporary IP interruption:

- Will be implemented when a predefined safety threshold has been met ([Section 6.6](#))
- May be considered by the investigator in the case of an AE/SAE or for another reason

If a temporary IP interruption occurred because a safety threshold was met, blinded treatment will be resumed at least 7 days later, either at a lower dose or with a permanent switch to placebo if the patient was at 5mg, as determined by the IWRS ([Section 6.6.3](#)).

If the IP was temporarily interrupted because of an AE/SAE, the investigator should make the best effort to resume IP as soon as practically possible, assuming there are no remaining safety concerns.

If dosing is interrupted for more than 3 consecutive days in the first 6 weeks and more than 7 consecutive days thereafter, the investigator should contact the Medical Monitor to discuss the patient.

All temporary IP interruptions of greater than 3 days should be recorded in the eCRF (stop and start dates and reason for interruption) and the Medical Monitor should be notified.

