9.4.9. Investigational Product Exposure

IP exposure will be summarized, including the total number of doses administered, total amount of drug administered, and the total duration of IP administration, defined as the date of the last dose minus the date of first dose + 1.

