6. STUDY POPULATION

6.1. Subjects Disposition

Patient disposition will be summarized based on all randomized patients. The following will be summarized:

- The number and percentage of patients who completed the study and the number of patients who discontinued from the study early,
- For the patients who discontinued from the study early, reasons for early discontinuation,
- The number and percentage of patients who received at least one dose of the IP,
- For the patients who received at least one dose of the IP, the number and percentage of patients who completed study treatment and the number of patients who discontinued the study treatment early,
- For the patients who discontinued the study treatment early, reasons for early discontinuation.

The number and percentage of randomized patients included in each analysis set will be summarized. Reasons for exclusion from analysis sets will be listed.

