7.7. Analysis of the Primary Efficacy Endpoint

7.7.1. Primary Efficacy Analysis

The primary endpoint is change in pVO₂ from baseline to Week 24. The **primary analysis** will be performed using an ANCOVA model that includes terms of treatment, randomization stratification factors (beta-blocker use status and CPET modality), baseline pVO₂ and baseline body weight as covariates in the FAS. [Table 5](#) below displays details of the two estimands for the primary endpoint.

Table 5: Estimands for Primary Endpoint

Attributes	Primary Estimand	Secondary Estimand
Population	FAS, target population of potentially treatable aficamten subjects.	Hypothetical target population of potentially treatable aficamten subjects continue with treatment and are capable of completing the Week 24 assessment. Subjects with missing Week 24 pVO ₂ due to intercurrent events or discontinuing treatment prior to Week 24 will be excluded.
Variable	Change from baseline to Week 24 in pVO ₂ . Data to be analyzed include all observed Week 24 pVO ₂ values from subjects who complete 24 weeks of treatment, or from subjects who early terminate from the treatment but remain in the study and have Week 24 pVO ₂ and imputed pVO ₂ for subjects who don't have Week 24 pVO ₂ . Imputation details are provided below.	Change from baseline to Week 24 in pVO ₂ . Data to be analyzed include observed pVO ₂ values from subjects who complete at least 24 weeks of treatment.
Measure of intervention effect	Mean treatment difference regardless of completing 24 weeks of treatment and experiencing intercurrent events.	Mean treatment difference among all subjects who remained on their randomized treatment for 24 weeks.

Subjects will be followed per the schedule of assessments from randomization through their final visit irrespective of whether the subject is continuing to receive study treatment. Reasons for not completing Week 24 CPET will be recorded on eCRF; categories of reasons include adverse

events, early termination, equipment failure, investigator decision, subject decision and other. The percentage of missing CPET data at Week 24 and the reasons for the missing data will be tabulated in the FAS. The following type of intercurrent events could preclude CPET at Week 24.

- Death
- Hospitalization
- CV AEs
- non-CV AEs (e.g., orthopedic injury)

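### Placebo weeks after an IWRS switch for LVEF <50% on 5 mg count as exposure in the aficamten arm, and the discontinuation counts do not show that active drug stopped

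*SAP*

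**What the plan says.** **The switch.** At Week 2, if LVEF is below 50%, "the IWRS will assign the patient to placebo" (Protocol 6.6.1.1). The Week 4, 6 and 8 sections and Protocol 6.6.2 do the same for a patient on Dose 1. The footnote to Protocol Table 4 repeats it for LVEF below 50% "on 5 mg, the patient will receive placebo", and adds that once a dose has been reduced "no further escalation is permitted". Protocol 6.6.2 rules out escalation after Week 6. For a restart after a safety-threshold interruption, Protocol 7.1 says blinded treatment resumes "either at a lower dose or with a permanent switch to placebo if the patient was at 5mg".

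**Exposure.** Protocol 9.4.9 summarises "the total duration of IP administration, defined as the date of the last dose minus the date of first dose + 1". The SAP 5.7.8 formula likewise ends at the last IP administration. Both safety-set definitions (Protocol Table 8, SAP 5.5.3) count placebo as IP.

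**Dose group.** SAP 5.7.8 classifies aficamten patients by the dose assigned at Week 8; they are "identified as 5 mg, 10 mg, 15 mg, 20mg or discontinuing IP prior to dose adjustment".

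**Disposition and tolerability.** SAP 6.1 reports "the number and percentage of patients who completed study treatment and the number of patients who discontinued the study treatment early". SAP 8.1 counts patients with TEAEs that led to early stopping of treatment.

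**Secondary estimand.** The effect-measure row of SAP Table 5 reads "Mean treatment difference among all subjects who remained on their randomized treatment for 24 weeks". Its Variable row takes observed values from anyone who finishes at least 24 weeks of treatment.

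**The concern.** Protocol 2.3.1 puts a fall in left ventricular systolic function first among the drug's risks, and LVEF-guided dosing is the main mitigation. Ending active drug because LVEF is below 50% at the lowest dose is therefore a tolerability outcome that a reader will look for. The derivation rules treat such a patient as someone who stays on study treatment. The exposure total for the aficamten arm then includes time on placebo, and the tables meant to show who stopped do not show this stop.

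The sites cannot repair this. Under Protocol 6.3 all site staff are blind to assignment and the dose is masked. Discontinuation and its reason come from the CRF (Protocol 7.2 and 9.4.7). An investigator who does not know that the tablets have become placebo cannot record that active drug ended. Only the IWRS holds that information, and outside the dose-titration summary (SAP 8.3.2) the SAP does not call on it.

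**Working it through.** The plan states no expected exposure and no expected switch rate, so there is no figure of its own to reproduce here. The stated power does reproduce: 121 per arm after 10% missing, a difference of 1.5 and an SD of 3.5 give 91.5% against the stated more than 90%. This point does not touch it.

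**Step 1: is the patient still on IP after the switch?** Yes on the main definitions. Placebo is IP in both safety-set definitions. Protocol Table 4 and 6.6.2 handle the switch as a dose reduction, and Protocol 7.1 describes blinded treatment as resumed. The reasons for permanent IP discontinuation in Protocol 7.2 do not name it, although that list is open-ended. The safety-set regrouping exception needs a different treatment throughout the study, so a switch partway through does not trigger it.

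**Step 2: one patient.** Formula (SAP 5.7.8): (last IP date − Day 1 + 1) / 7. For a patient who takes IP for 168 days, 168 / 7 = 24.0 weeks whatever the switch date. Ending the same formula at the last aficamten dose gives:

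| Switch at | Weeks by SAP formula | Weeks on aficamten (about) | Excess |
|---|---|---|---|
| Week 2 | 24 | 2 | 22 |
| Week 8 | 24 | 8 | 16 |
| Week 20 | 24 | 20 | 4 |

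**Step 3: the arm.** Protocol 9.2 plans about 135 aficamten patients, so the full arm is 135 × 24 = 3,240 patient-weeks. The number switched is an assumption, taken here as 0 to 4. Phase 2 had LVEF below 50% in 2 of 41 aficamten patients across all doses (Protocol 2.3.1). One was reduced from 20 mg and the dose of the other is not given, so no case at 5 mg is documented.

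- None switched: excess 0.
- One switched at Week 2: 22 / 3,240 = 0.7%.
- Four switched at Week 20: 4 × 4 = 16; 16 / 3,240 = 0.5%.
- Four switched at Week 2: 4 × 22 = 88; 88 / 3,240 = 2.7%, or 88 / 135 = 0.65 weeks on the arm mean.
- Active-drug stops missing from the discontinuation counts: 0 to 4 / 135 = 3.0%.

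**Step 4: the other tables.** Actual Dose Group is fixed by the Week 8 assignment. A patient switched at or before Week 8 is neither on 5 to 20 mg nor off IP, so no category fits. A patient switched later keeps the Week 8 dose by design. In Table 5, a switched patient who takes tablets to Week 24 satisfies the Variable row but arguably not the effect-measure row.

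**The case against.** The strongest reply is that the plan already reports the safety signal. SAP 8.2.2 counts LVEF below 50% and below 40% by patient and by event in each arm, and SAP 2.2.4 does so for the site read, the core laboratory read and both. SAP 8.3.2 tabulates IWRS dose by visit and by last titrated dose, and either display could show the switch. The row categories may be settled in the display specifications, which are a separate document. The protocol treats the switch as a dose reduction, so reporting it with titration is consistent with the design. All of this stands. A reader might infer that low LVEF goes unreported, or that removal from active drug is certain to appear as zero. The documents do not support either. What is missing is a named placebo level for the active arm (SAP Table 1 lists only 5 to 20 mg) and any count of stops of active drug.

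A second reply is that SAP 3.2 glosses IP as aficamten, with placebo beside it. The last IP date could then mean the last aficamten dose. That reading leaves the placebo arm without an exposure period, and it conflicts with SAP 5.5.3. It shows that the term needs fixing, not that the formula is safe.

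Three further inferences also go too far.

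- A reader might conclude that adverse events after a switch are assigned to the wrong dose. SAP 8.1 uses dose level at onset, and nothing carries 5 mg forward. The level is unnamed, not wrong.
- A reader might conclude that the secondary estimand definitely includes switched patients. Its two rows point in different directions, so it is ambiguous. It is also a supportive analysis outside the testing hierarchy.
- A reader might take 2 of 41 as the expected switch rate. It covers all doses and says nothing about 5 mg.

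**Conclusion.** The point holds for exposure duration and for stops of active drug. As written, the exposure formula gives a wrong aficamten duration for every switched patient who continues taking tablets, by about 4 to 22 weeks for switches between Week 20 and Week 2. The discontinuation counts in SAP 6.1 and 8.1 do not show that active drug ended. The gap in Actual Dose Group is narrower: it covers only switches up to Week 8, in a variable that the SAP reserves for selected displays. Table 5 needs clarifying.

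The effect on the arm is small and uncertain. It is 0 to 88 of about 3,240 patient-weeks, assuming 0 to 4 switches among 135 patients; the top of the range requires every switch to be at Week 2. Total drug amount (Protocol 9.4.9) and total exposure (SAP 8.3.1) are not defined closely enough to say whether they share the error. The primary analysis, its power and the multiplicity-controlled tests are unaffected. The change is still worth making because it concerns the drug's main risk and costs little.

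**What to change.** Amend the SAP before database lock.

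- **SAP 5.7.8 and 8.3.1:** report aficamten exposure to the last active dose beside IP exposure, using IWRS assignment dates after unblinding.
- **Levels:** add a level for patients switched to placebo by the IWRS to Actual Dose Group, last titrated dose, dose by visit and dose level at AE onset.
- **SAP 6.1 and 8.1:** tabulate the number and timing of active-drug stops for LVEF in the aficamten arm, whether by IP discontinuation or by IWRS switch. Show beside them the placebo-arm patients who met the same LVEF rule on Dose 1, because the stop itself cannot occur in that arm.
- **Table 5:** reconcile the two rows by stating one rule for switched patients, with a matching rule for placebo patients who meet the same criterion. Removing only aficamten patients on a post-randomization LVEF value would make the comparison asymmetric.

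Leave the dosing rules and the primary estimand unchanged. The cost is SAP wording and programming; the IWRS already generates the assignment dates. The downside for the sponsor is that the aficamten stop rate will look slightly less favourable.
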